1. STUDY OBJECTIVES/HYPOTHESIS

Primary Objective(s)

To enhance and test our ED SexHealth intervention that provides risk reduction counseling and point-of-care services as well as connections to sustainable, non-episodic sources of care.

Hypothesis 1: The enhanced ED SexHealth intervention will result in statistically significantly higher health service uptake rates versus a standard information arm.

Hypothesis 2: The enhanced ED SexHealth intervention will be feasible, as measured by qualitative and quantitative data from adolescents, health educators, ED providers and hospital administrators.

2. BACKGROUND and RATIONALE

Although highly preventable, STIs/HIV and unintended pregnancy are significant and costly public health problems that disproportionately impact adolescents, especially minority and uninsured youth.¹⁻³ While these disparities result from a complex convergence of patient, provider, and health systems factors, limited access to care directly contributes to these disparities, independent of race/ethnicity.⁴⁻⁸ Adolescents make 19 million Emergency Department (ED) visits each year and frequently report intercourse not protected against STI/HIV or pregnancy.⁹⁻¹⁰ Further, among these youths, rates of infection with chlamydia and gonorrhea are up to 7 times higher than the general population.¹¹⁻¹⁴

One non-traditional setting for targeted interventions is the ED. ED-based interventions are feasible because most adolescent visits are not urgent and, in fact, youth commonly present with sexual health concerns.¹⁰ For several million high-risk adolescents, the ED is their only or primary contact with health care.¹⁰ As such, there is growing support to use the ED to improve adolescent sexual health outcomes, specifically calling for contraception, behavioral counseling, and links to ongoing care.¹⁶⁻¹⁹ The ED has been used successfully to target aspects of adolescent health, but most sexual health efforts have focused only on *testing* for STIs/HIV.¹¹⁻¹³ Routine HIV testing in EDs has been well received by adolescents and guardians.²⁰⁻²⁴ Recently, a clinical decision support (CDS) system was used in two EDs to improve testing rates for STIs/HIV.^{12,22} Computerized CDS systems use patient characteristics to generate tailored recommendations, are a scalable strategy for health promotion, may increase patient disclosure of risk factors, and are effective at overcoming barriers such as time constraints and knowledge gaps.²⁵⁻²⁹ CDS systems may increase testing acceptance, but without the accompanying provision of behavioral counseling to increase preventive behaviors, their use is unlikely to lead to reductions in STIs/HIV or unintended pregnancy.

This proposal addresses a major gap in health care access for this vulnerable population and is consistent with Healthy People 2020 objectives, to “promote healthy sexual behaviors, strengthen community capacity, and increase access to quality services to prevent STIs.”¹⁵ It will lay the groundwork for a large-scale trial of the intervention. By connecting the highest-risk adolescents with point-of-care services and sources for care, this proposed work is significant because our ED SexHealth intervention has potential to reduce disparities in STIs/HIV and unintended pregnancy as well as risks for long-term sequelae including pelvic inflammatory disease, infertility, and cervical cancer. The prevention of STIs/HIV and unintended pregnancy, together with prevention of life-threatening illnesses and social consequences, could result in significant decreased costs for adolescents, families, and society.

Preliminary work

We have completed two small, open trials (CMH-IRB #'s 15090399 and 14060265) of the SexHealth intervention. In version 1, 20 sexually experienced patients aged 14-19 years presenting to our ED received motivational interviewing from a dedicated health educator to foster engagement in safer sex behaviors and completion of sexual health services. The intervention included agenda setting, exploration of behaviors, decisional balance exercises, tailored feedback and health service provision (i.e., condoms, emergency contraception [EC] prescription for future use, testing for pregnancy/sexually transmitted infections [STIs], and Adolescent Clinic referral). Mean intervention length was 15.7 minutes. Most (65%) participants completed ≥ 1 service. Most (78%) reported that the interventionist maintained high fidelity to intervention principles and most (80%) were very satisfied with the intervention.

In version 2, we developed a computerized clinical decision support (CDS) system to enhance service delivery from the dedicated health educator. The enhanced intervention, conducted by the same educator as version 1, included the same intervention components and the CDS system which used patient-entered behavioral data to create tailored, evidence-based service recommendations for educator use during the intervention. In this version, we also dispensed EC medication directly to patients (rather than prescriptions) for immediate and/or future use and provided medication for untreated, patient-reported STIs. For 32 participants in this open trial, the CDS system generated a total of 124 recommendations, 3.9 recommendations per participant. The educator discussed 77% of all recommendations. Most (75%) participants had uptake of ≥ 1 health service, which was an improvement from the pilot study (65%) but not statistically significant ($p>0.05$). Nearly all (93%) were satisfied with their recommendations and 100% were satisfied with the counseling session. The educator rated the system-generated recommendations as “very” useful (94%) and “very” easy to use (91%).

In order to improve health service uptake and facilitate safer sex behaviors, we will again enhance our SexHealth intervention by including: 1) improved use of motivational techniques, 2) additional ED-based services (i.e., HIV testing, regular hormonal contraception), 3) condom skills training, and 4) an expanded clinical decision support system to generate tailored service recommendations (i.e., dynamically adaptive checklists) for use by the health educator.

3. STUDY DESIGN

This is an adaptive trial with an initial **Formative Revision Process** followed by a **Randomized Controlled Trial**. Up to 500 adolescents will be consented into this study to achieve 6 completed subjects for the formative process and 80 completed subjects (40 in each arm) for the RCT. Up to two Health Educators will be consented as secondary subjects who will complete post-intervention assessment survey's.

Formative Revision Process

Based on pilot feedback and relevant literature,¹⁹⁻²³ we made modifications to increase adolescents' motivation for service uptake and safer sex behaviors. To increase motivation, we will: 1) expand opportunities to increase receptiveness to change, 2) emphasize interpersonal skills for educators, 3) increase opportunities to develop discrepancy between behavior and risk, and 4) emphasize need for regular care and how to access it. We will incorporate CDS system-generated recommendations directly into the intervention to facilitate participant risk

comprehension and standardize service provision. We will add behavioral skills training and role play for condom use. The educator will deliver the revised SexHealth intervention with a formative group of 6 adolescents. We will gather feedback on intervention acceptability and feasibility using individual session analysis and in-depth interviews. Sessions will be audio-recorded and coded to provide educator feedback and evaluate fidelity to core MI skills. Each adolescent will also complete an in-depth post-intervention interview, with a separate team member. Interviews will be audio-recorded and written notes taken. Data from session analysis, interviews, and educator feedback will be incorporated into the final version with a targeted length of 30 minutes. Our intervention manual contains highlights of revisions, including tailoring for sexual minorities.

The study will then continue as a two-armed randomized controlled, parallel group design with 80 completed participants.

Randomized Controlled Trial

The **Control Group** will receive a printed health pamphlet and a list of local resources with the phone number for Adolescent Clinic. Participants will then be referred back to their ED provider, who will provide their standard care.

The **Intervention Group** will receive the same pamphlet as controls and the enhanced ED SexHealth intervention with the educator. Based on behaviors, CDS system recommendations (generated from screening survey responses only for intervention participants), and discussions, participants may be offered testing (for pregnancy, gonorrhea/chlamydia, and/or HIV), hormonal birth control, condoms, emergency contraception (for immediate or future use), treatment for previously diagnosed (yet untreated) infection with gonorrhea/chlamydia, and a scheduled appointment at Adolescent Clinic (for ongoing care, including repeat STI/HIV testing if needed). All services will be provided at point of care, costs will be covered by the study. We will use urine/swab specimens for STI testing (Gen-Probe Inc.) with results available within 7 days. We will contact those with an STI and advise them to seek care at the hospital-affiliated Adolescent Clinic or we can call in a prescription for treatment of Chlamydia. We will use fingerstick blood for HIV testing (Alere North America Inc.) and for those with a reactive screen, we will provide immediate, in-person counseling with a case manager from our community partner (see letter from KC CARE Clinic), obtain a confirmatory test, and arrange for rapid follow-up.

Health Educator

We will recruit a health educator with training in public health and health behavior change. They will receive training including in-depth Motivational Interviewing (MI) training supervised by expert team members. Training will include mock patients for hands-on practice and immediate feedback. Encounters will be audio-taped and coded using the Motivational Interviewing Treatment Integrity Coding system to provide objective feedback. The educator will receive instruction in adolescent sexual health including HIV/STIs, sexual minority issues, contraception, and HIV counseling and testing (in partnership with KC CARE Clinic and the Midwest AIDS Training and Education Center). The educator will discuss the first 6 trial participants with Drs. [name] and [name] and attend a one-day “booster” training halfway through the study (led by Drs. [name] and [name]). All sessions will be audio-recorded; 20% will be randomly selected and evaluated for MI fidelity using accepted techniques.¹⁰²⁻⁰³

Provision of health services

Participants may be offered testing (for pregnancy, gonorrhea/chlamydia, and/or HIV), hormonal birth control, condoms, emergency contraception (for immediate or future use), treatment for previously diagnosed (yet untreated) infection with gonorrhea/chlamydia, and a scheduled

appointment at Adolescent Clinic (for ongoing care, including repeat STI/HIV testing if needed). The participant then selects which (if any) of these recommendations s/he wants to receive/complete. Urine pregnancy testing will be conducted at the time of the ED visit. For STIs, urine specimen or swab (from throat, rectum, or vagina) will be collected, labeled with study ID number, and stored in the hospital laboratory. The nucleic acid amplification tests will be performed according to manufacturer's directions and testing will occur every few days (Aptima Combo-2; Gen-Probe Inc., San Diego, CA). Subjects with an STI will be contacted and advised to seek treatment, preferably at the Adolescent Clinic where treatment is free. We will use fingerstick blood for HIV testing (Alere North America Inc.) and for those with a reactive screen, we will provide immediate, in-person counseling with a case manager from our community partner (see letter from KC CARE Clinic), obtain a confirmatory test, ([Mayo \(test code HIVDI- HIV-1 and HIV-2 Antibody Confirmation and Differentiation, Serum\)](#) and arrange for rapid follow-up. We will follow state statutes for reporting Chlamydia, gonorrhea and HIV infections.

Process for Medication Provision

The provision of medication will be a collaborative process involving the participant, the educator and the study team. For any prescription medication, the health educator will discuss the medication with an ED physician or nurse practitioner. That provider will review the medication(s) with the educator and place the order within Cerner. The ED provider may decide that a medication desired by the participant or recommended by the system is not appropriate and refuse provision (e.g., in case of drug allergy).

Data Collection /sources

We will collect immediate post-intervention survey data from all participants. The health educator will complete a survey following each intervention. We will collect data on health services (i.e., STI/pregnancy testing, condoms, emergency contraception, hormonal contraception, STI treatment, HIV testing, referral to clinic) offered, accepted, and completed as well as services provided as part of ED clinical care. When determining completion of sexual health services, services that are completed via a standing order or protocol (e.g., adolescent female receiving urine pregnancy test before radiographic imaging) will be noted and not included when determining our outcome measurement.

Incentives

Compensation for the formative group will be up to \$55.00.

Part 1 Take survey	Part 2 Meet with the Health Educator	Part 3 Take survey about meeting with the Health Educator
\$5.00	\$30.00	\$20.00

Compensation for the RCT will be up to \$80:

\$5 for completing the screening survey, if the subject does not qualify or decides not to continue in the study, their participation will be over and they will receive a \$5.00 Target® gift card.

If a subject qualifies to continue in the study and signs the written consent they will receive a Greenphire Clincard instead of the Target® card. If they continue in the study they will be randomized into study group. At the end of this visit they will receive the Greenphire Clincard gift card. It will be uploaded with \$5.00 for taking the computerized survey and \$30 for completing the randomization part of the visit for a total of \$35.00. An additional \$10-each will be loaded onto the Greenphire Clincard when month 2 and month 4 surveys are completed and final \$25 for month 6 survey completion. All surveys can be completed online or by telephone. All health services (e.g., STI testing, condoms) will be provided at no cost to participants in the intervention arm. Charges for any service for participants in the control arm will be billed by the ED provider according to their standard practice.

Visit 1 (screening)	Visit 1 (randomization)	2 mo.	4 mo.	6 mo.
Take computerized screening survey \$5.00	Be randomized into study group and complete assigned arm procedures \$30.00	Take survey online or by phone \$10.00	Take survey online or by phone \$10.00	Take survey online or by phone \$25.00

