5. DATA COLLECTION

Surveys will be administered via REDCap, which enables administration of online surveys via a secure website utilizing a secure sockets layer (SSL) protocol. Electronic data will be stored in an encrypted format on hospital firewall-protected servers, written data will be stored in a locked office. Direct data entry provides a confidential means of survey administration, consistent delivery, and enhanced data accuracy.^{49,50} Data from clinical records will be electronically extracted from hospital databases. Participants will be assigned an anonymous study number. Surveys will be completed confidentially and will not contain identifying information. Contact information will be recorded separately, via a separate REDCap data collection tool, and will be used for notification of test results. This data will include medical record number, date of birth, address, and phone number. We do not plan on collecting social security number as we feel this study will qualify for exemption from Greenphire and have requested exemption. In order to better evaluate the over-all adolescent population in the Main ED we will be collecting refusal data from those potential subjects and their parents who decline to participate.

Secure Storage of Data

Records to be kept and Secure Storage of Data: Survey development, data collection and handling will be conducted through Children's Mercy's REDCap Research software. The Redcap database is protected by Gazzang's zNcrypt product. zNcrypt transparently encrypts and secures data at rest without any changes to your applications or database and ensures there is minimal performance lag in the encryption or decryption process. Advanced key management and process-based access controls enable organizations to meet compliance regulations and ensure unauthorized parties or malicious actors never gain access to the encrypted data. zNcrypt meets compliance for HIPAA, PCI-DSS, FISMA, EU Data Protection, and more.

Data will be exported from REDCap to statistical programs for analysis (i.e. SAS, SPSS, Excel.) All data will be securely stored on password-protected servers. Only personnel involved in the study will have access to the data. Data transfer between members of the study team will be conducted solely within the confines of the CMH network.

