7. STATISTICAL CONSIDERATIONS

The **Primary Outcome Measure** is the proportion of participants in each arm who receive any health service (i.e., STI/pregnancy/HIV testing, condoms, emergency or other hormonal contraception, Adolescent Clinic referral/visit completion). Visit completion will be measured at 3 weeks; all others at initial ED visit.

Feasibility Measures: All participants: (1) proportion of eligible patients enrolled; (2) proportion rating screening survey as very/fairly satisfactory; and (3) proportion completing follow-up. Intervention arm: (1) proportion completing intervention; (2) proportion in which 75% of recommendations are discussed; (3) proportion rating intervention as very/fairly satisfactory; and (4) counseling session time. We will examine length of stay for participants vs. non-participants and costs.

We use items adapted from national surveys to assess risk behaviors. We will use an audio computer-assisted self-interview (ACASI) to reduce social desirability bias and literacy barriers. Follow-up will be completed via web-based surveys or telephone.

Sample size: In a review of 130 patients, we found the pre-intervention proportion of ≥ 1 service uptake was .08. Our pilot study provided an estimate of the post intervention proportion of .65. We used conservative estimates for differences in uptake rates between arms, inflating the control to .15 (vs. .08), deflating the intervention to .50 (vs. .65). With these estimates, an alpha of .05 and a sample size of 76 participants (38 each arm) we achieve a power of .94, well above the usual .80. Given that our primary outcome will be measured at 3 weeks, and our historical attrition rate has been low, we will recruit only four additional participants (N=80) to protect against attrition. Even with 25% attrition, we would still achieve .84/.91 power for two-tail and

one-tail tests respectively. To protect against self-selection or attrition biases, we will randomize arm assignments and analyze potential impacts of attrition.

Hypothesis: The enhanced ED SexHealth intervention will result in statistically significantly higher health service uptake rates versus a standard information arm.

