APPENDIX 1.

STUDY SCHEMA

FORMATIVE GROUP

PROCEDURE	Part 1 BASELINE Survey	Part 2 INTERVENTION	Part 3 POST-INTERVENTION Survey
Adolescents who meet Part 1 Base-line Inclusion criteria and have no exclusion criteria will be approached and invited to participate in the research study. Research Study Information FORMATIVE GROUP given to parent	X		
Obtain permission to interview teen alone	X		
Obtain verbal consent for FORMATIVE GROUP baseline screening from teen	X		
Teen completes computerized baseline screening survey	X		
Teen meets Part 2 INTERVENTION inclusion criteria	X		
FORMATIVE GROUP Written Consent Obtained		X	
Meets with Health Educator for Part 2 INTERVENTION including Health services offered and		X	
Post-intervention Survey to assess satisfaction with intervention			X

RANDOMIZED CONTROL TRIAL STUDY SCHEMA

PROCEDURE	At Initial ED Visit					
	BASELINE Survey	INTERVENTION	Post INTERVENTION Survey	3 weeks post ED visit	2 and 4 months post ED visit	6 months post ED visit
Adolescents who meet Part 1 Base-line Inclusion criteria and have no exclusion criteria will be approached and invited to participate in the research study. RCT Information given to parent	X					
Obtain permission to interview teen alone	X					
Obtain verbal consent for RCT baseline screening from teen	X					
Teen completes computerized baseline screening survey	X					
Teen meets Part 2 INTERVENTION inclusion criteria	X					
Teen is randomized to either the CONTROL ARM or the INTERVENTION ARM and consented with the appropriate consent form		X				
Meets with Health Educator for Part 2 INTERVENTION		X				
Teen takes post-intervention satisfaction survey			X			
Health Educator fills out post intervention assessment			X			
Medical Chart reviewed for health services utilization by study team				X		
Teen completes brief survey on: sex health behaviors, healthcare utilization, readiness for safer sex					X	X
Assessment of new occurrence of STD or HIV During survey						X

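### The primary outcome leaves out ED services done by standing order or protocol, but the plan gives no list of such orders, no named classifier and no masking to arm

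*Combined protocol and SAP*

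**What the plan says.** Section 7 defines the primary outcome as "the proportion of participants in each arm who receive any health service" and sets its timing: "Visit completion will be measured at 3 weeks; all others at initial ED visit". Section 3 (Data Collection/sources) has the study record services offered, accepted and completed, including those given in ordinary ED care. It then removes some of them: "services that are completed via a standing order or protocol" "will be noted and not included when determining our outcome measurement". The only guidance on applying this is one example ("e.g., adolescent female receiving urine pregnancy test before radiographic imaging"). The rule names neither an arm nor a person who applies it.

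On sources, Section 5 says "Data from clinical records will be electronically extracted from hospital databases". The trial schema in Appendix 1 has, at 3 weeks, "Medical Chart reviewed for health services utilization by study team". Section 3 adds "The health educator will complete a survey following each intervention", which has no counterpart in the control arm. Masking of any assessor is not mentioned anywhere in the supplied text.

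**The concern.** Under this rule the same urine pregnancy test is either a success or nothing, depending on why it was ordered. That has to be judged after allocation, and randomization does not protect a judgement made by someone who knows the arm.

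The arm would be easy to see. Appendix 1 has participants sign the consent form for their assigned arm, decision-support recommendations are generated only for the intervention arm, and educator surveys exist only for intervention sessions. Unless these markers are removed, whoever combines the sources is likely to learn the allocation.

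Section 4 suggests that the question will come up. The trial balances genitourinary complaints between arms because earlier work found that they affect STI and pregnancy testing.

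A lean towards calling a control's ED test protocol-driven would lower control uptake and widen the difference. Sections 7 and 9 intend the results to supply effect-size estimates for a multi-site trial application, so a bias here would carry forward.

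**Working it through.** **Inputs.** From Section 7: control .15, intervention .50, alpha .05, 38 per arm for power, a comparison of two sample proportions, and observed rates of .08 and .65. From Section 3: 40 per arm. The documents give no misclassification rate, so every such rate below is an assumption.

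**1. The plan's power.** The unpooled standard error with 38 per arm is √[(.15×.85 + .50×.50)/38] = .0997. Power is Φ(.35/.0997 − 1.96) = .94, as stated. With 25% attrition (30 per arm), the pooled formula gives .843 two-sided and .911 one-sided, matching the stated .84/.91. The concern does not rest on a sample-size error, and the fix changes neither N nor power.

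**2. Robustness at the planning values.** The expected counts are .15×40 = 6 and .50×40 = 20. The test is z = (p₂ − p₁)/√[p̄(1−p̄)(2/40)], two-sided.

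| Control v intervention | p̄ | z | p (z test) | p (Fisher) |
|---|---|---|---|---|
| 6/40 v 20/40 | .325 | 3.34 | .0008 | .0016 |
| 11/40 v 20/40 | .3875 | 2.07 | .039 | .066 |
| 12/40 v 20/40 | .400 | 1.83 | .068 | .110 |

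Six control successes (five by Fisher) would have to be restored before significance is lost. Six equals the whole expected control count.

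**3. Error rate with no true effect.** Assume that both arms have true uptake p and that a fraction f of control successes, and none in the intervention arm, is wrongly struck. The control rate becomes p(1−f). The rejection rate of the two-sided z test comes from summing exact binomial probabilities at 40 per arm.

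| True uptake | f = 0 | f = .20 | f = .30 |
|---|---|---|---|
| .08 | .058 | .065 | .076 |
| .15 | .053 | .073 | .099 |
| .30 | .048 | .091 | .150 |

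At .15, f = .20 to .30 means 6×.20 = 1.2 to 6×.30 = 1.8 participants on average. At .30 it means 12×.20 = 2.4 to 12×.30 = 3.6. If 20% is struck in both arms at .30, the rate is .050. The inflation therefore comes wholly from the assumed control-only error.

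**4. Whose outcome do the calls decide?** A call changes the outcome only if the participant has no other counted service. Assume that 20% in each arm have a protocol service, independently of other uptake.

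- At .15/.50: control 40×.20×.85 = 6.8; intervention 40×.20×.50 = 4.0. The intervention share is 4.0/10.8 = 37%.
- At .08/.65: control 40×.20×.92 = 7.4; intervention 40×.20×.35 = 2.8. The intervention share is 2.8/10.2 = 27%.

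The 20% cancels from these shares. The tilt towards controls appears even with a perfectly even-handed assessor.

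**The case against.** A reader might infer several stronger claims that the documents do not support.

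- **That an unmasked study team makes the call.** The plan is silent on masking; it does not say that anyone is unmasked. Appendix 1 names the study team only for the 3-week chart review, and nobody is named for the standing-order call. What stands is that both points are unspecified while trial records show the arm.
- **That the calls fall almost only on controls.** The rule covers both arms. At the planned .50, half of intervention participants have no counted service, so the call is just as decisive for them. Part of the tilt is definitional, and masking would not remove it.
- **That the 3-week review is biased in the same way.** At 3 weeks the outcome adds only clinic visit completion. That is a recorded fact and nothing is struck out.
- **That a few calls would readily produce a false positive.** Moving from 11/40 v 18/40 (p=.10) to 8/40 v 18/40 (p=.017) does cross .05 with three calls, but those counts were picked because they straddle it. At the plan's own control rates of .08 and .15 the inflation is modest.

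It is also fair that the components are discrete tests or supplied items and that clinical data are extracted electronically, which limits discretion over whether a service took place. Nothing in the plan says that the extract records why a service was ordered, and the rule turns on that reason. The plan does have excluded services noted, so a reanalysis that counts them is possible, but none is specified.

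**Conclusion.** The concern holds in a limited form. The plan does not say who classifies ED services as standing order or protocol, by what list, or whether that person is masked, and the primary outcome depends on the answer. Assessor bias after randomization is possible. A direction against controls is plausible but not established.

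At the planning values the conclusion would survive moderate misclassification. The exposure is greater if the true effect is small or absent: on the assumption that 20% to 30% of control successes alone are wrongly struck, the .05 error rate becomes about .07 to .10 at 15% uptake and .09 to .15 at 30%. These are illustrations, not estimates. The change is worth making because it is cheap and the judgement sits inside the primary outcome.

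**What to change.** Amend Section 3 (Data Collection/sources) and Section 7 (Primary Outcome Measure) as follows.

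1. Before the data are opened, fix a list of the orders and circumstances that count as standing order or protocol.
2. Have an existing team member without access to the allocation classify ED clinical-care testing and treatment orders for all randomized participants against that list. The source is the planned electronic extract with arm and study-service markers removed. Merge arm and educator-supplied services afterwards. Take clinic visits directly from the record, without classification.
3. Add a sensitivity analysis of the primary outcome that counts the noted standing-order or protocol services in both arms. This shows how far the result depends on the exclusion, including the definitional part that masking cannot address.

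The cost is a short amendment and some data preparation. Sample size, power and participant procedures do not change. Masking may be incomplete where the chart mentions the study, or where an ED provider placed an order after talking with the educator, so the fixed list and the sensitivity analysis are needed as well.
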